6.13.1. Recommended Phase 2 Dose Determination

The RP2D will be a dose at which at least 10 patients, but no more than 20, have been enrolled. The RP2D will be agreed upon following discussion between the investigators and the Lilly CRP or CRS and will include an assessment of safety, PK, and PD data. At the RP2D, the intersection of the number of patients dosed and the number of DLTs at that dose level on the mTPI grid should indicate “S” or “E”.

6.13.2. Extent of Exposure

For doses less than 1000 mg, LY3164530 will be administered intravenously over approximately 60 minutes on Days 1 and 15 of each 28-day cycle. The Sponsor may instruct sites to extend the infusion time for up to 3 hours for doses ≥ 1000 mg. The assigned dose and duration of infusion of LY3164530 will be provided by the Sponsor on a patient registration form. Subsequent doses and/or infusion times should be adjusted as described in Protocol Section 7.2.5.

A patient is said to have received a cycle if they received some of the scheduled/planned dose of study treatment in the cycle. A patient is said to have completed a cycle if they received all of study treatment planned for this cycle. The number of patients receiving/completing a given number of cycles will be presented by dose level and overall in a summary table, as well as by patient.

The number of dose reductions, dose delays, and number of cycles received will be summarized for all treated patients by cohorts. The number of patients with any dose reductions and delays will be presented overall as well as for each cycle by cohorts.

6.13.3. Adverse Events

Common Terminology Criteria for Adverse Events (CTCAE) Version 4.03 will be used to grade all AEs and other symptoms. Minor updates to the CTCAE Version 4.03 from the NCI will not necessitate a protocol amendment, and the use of an updated CTCAE Version 4.03 will not be considered a protocol violation. For AEs without matching terminology within the NCI-CTCAE v 4.03 criteria, the investigator will be responsible for selecting the appropriate System Organ Class (SOC) and assessing severity grade based on the intensity of the event. The verbatim text for these AEs will be coded according to the available version of the Medical Dictionary for Regulatory Activities (MedDRA).

A treatment-emergent adverse event (TEAE) is defined as (i) adverse event that occurred after the administration of at least one dose of study therapy, regardless of causality; or (ii) adverse events already present during screening that worsen following exposure to the treatment, regardless of causality. All analysis of AEs will be done according to the MedDRA hierarchy and the investigator assigned CTCAE term will be used as the assigned LLT, except where “other-specify” has been chosen, in which case the LLT will come from the centrally mapped verbatim description of the event. Event worsen in severity is supported by higher CTCAE grade observed after first dose of study treatment for the corresponding MedDRA Lower Level Term (LLT). Treatment-emergent adverse events (AEs) will be aggregated and summarized by MedDRA System Organ Class (SOC) and Preferred Term (PT).

The number of patients who experienced a TEAE, SAE, TEAE related to study drug, died, or discontinued from the study due to an AE will be summarized. Treatment-emergent adverse events will be summarized by SOC, by decreasing frequency within SOC, and by maximum CTCAE severity grade, including the total of patients with maximum severity grade ≥ 3 .

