6.2. Summary of Study Design

Study JNBA is a multicenter, nonrandomized, open label, dose escalation Phase 1 study of IV LY3164530 in patients with advanced and/or metastatic cancer. Eligible patients will receive LY3164530 as an infusion on Days 1 and 15 (Schedule 1) or on Days 1, 8, 15, and 22 (Schedule 2) of each cycle. A cycle will consist of 28 days and the schedules will enroll in parallel.

Dose escalation will be driven by a modified toxicity probability interval (mTPI) method. The RP2D and schedule will be determined once at least 10 patients, but no more than 20, are treated at a dose and schedule that is at or below the maximum tolerated dose (MTD). The actual sample size for Study JNBA is anticipated to be approximately 50 patients depending on the incidence of DLTs.

The planned duration of treatment is 2 cycles. Patients who are receiving benefit from study drug may continue to be treated with LY3164530 until 1 or more of the criteria for discontinuation have been fulfilled (Section 6.3.1).

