6.2.1. Primary Endpoint Analysis, Study Completion, and End of Trial

The primary endpoint analysis will occur after the final patient enrolled has been evaluated for at least 1 cycle. Any patient enrolled that has completed at least 1 cycle of treatment or discontinued due to an AE (during Cycle 1), and completed the required post-treatment safety assessment, will be considered to have completed the study. However, additional cycles of therapy may continue as long as the patient is receiving benefit and no criteria for discontinuation have been met. All secondary/exploratory endpoint analyses will be updated at study completion.

Both the study completion and end of trial will be the date of the last visit or last scheduled procedure for the last patient.

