7.2.3. Recommended Phase 2 Dose Determination

The RP2D will be a dose at which at least 10 patients, but no more than 20, have been enrolled. The RP2D will be agreed upon following discussion between the investigators and the Lilly CRP or CRS and will include an assessment of safety, PK, and PD data. At the RP2D, the intersection of the number of patients dosed and the number of DLTs at that dose level on the mTPI grid should indicate “S” or “E.”

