5.1. Summary of Study Design

Study I7H-MC-JNBA (JNBA) is a multicenter, nonrandomized, open label, dose escalation Phase 1 study of IV LY3164530 in patients with advanced and/or metastatic cancer. Eligible patients will receive LY3164530 as an infusion on Days 1 and 15 of each cycle. A cycle will consist of 28 days.

The planned duration of treatment is 2 cycles. Patients who are receiving benefit from study drug may continue to be treated with LY3164530 until 1 or more of the criteria for discontinuation have been fulfilled (Protocol Section 6.3.1).

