6.1. General Considerations

The analyses for this study will be descriptive, except for possible exploratory analyses as deemed appropriate. Data analyses will be provided by dose levels and for all patients combined wherever appropriate. For continuous variables, summary statistics will include number of patients (N), mean, median, standard deviation (SD), standard error (SE), minimum, and maximum. Categorical endpoints will be summarized using N, frequency, percentages, and associated SE.

Exploratory analyses of the data that are not described in the protocol will be conducted as deemed appropriate.

Any change to the data analysis methods described in the protocol will require an amendment ONLY if it changes a principal feature of the protocol. Any other change to the data analysis methods described in the protocol and the justification for making the change will be described in the clinical study report (CSR).

The interpretation of the study results will be the responsibility of the investigator with the Lilly CRP and/or CRS, pharmacokineticist, and statistician. The CRP and/or CRS and statistician will also be responsible for the appropriate conduct of an internal review for both the final study report and any study-related material to be authorized by Lilly for publication.

The following data handling conventions will be used in the analysis:

Table JNBA.6.1. Data Handling Conventions and Rules

Term	Definition or Rule
Study Day	If assessment is on or after date of first dose then (date of assessment) – (date of first study drug dose) +1
	If assessment precedes first dose of drug then (date of assessment) – (date of first study drug dose)
	There is no study day 0. Study day 1 is the date of first dose and study day -1 is the day before the first dose.
Cycle Day	If assessment is on or after date of first dose in the cycle then (date of assessment) – (date of first study drug dose in cycle) +1
	If assessment precedes first dose of drug in a cycle then (date of assessment) – (date of first study drug dose in cycle)
	There is no cycle day 0. Cycle day 1 is the date of first dose in the cycle and cycle day -1 is the day before the first dose.

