6.13.5. Clinical Laboratory Evaluation

Laboratory data (including chemistry, hematology, and coagulation) will be summarized for all patients on therapy. Relevant hematology and chemistry laboratory values will be graded according to CTCAE Version 4.03. The grades will be summarized by the maximum grade over the entire study for all patients on therapy.

Abnormal laboratory results will be summarized for all patients on therapy by cycle. To the extent that they can be assessed according to CTCAE Version 4.03 specific grades, these abnormal lab results will be summarized by cohort and cycle independent of clinical findings determined by the investigator. International System of Units (SI units) will be presented in all outputs.

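### Adverse events are tabulated as crude worst-grade counts over unequal follow-up, which can make the more recently enrolled dose or schedule look safer when the RP2D is chosen

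*SAP*

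**What the plan says.** **Adverse events.** SAP 6.13.3 plans counts of patients: "Treatment-emergent adverse events will be summarized by SOC, by decreasing frequency within SOC, and by maximum CTCAE severity grade". A treatment-emergent adverse event (TEAE) includes any "adverse event that occurred after the administration of at least one dose of study therapy, regardless of causality", and the definition gives no end to the window. No TEAE table is split by cycle or related to exposure. For laboratory grades SAP 6.13.5 is explicit: "The grades will be summarized by the maximum grade over the entire study for all patients on therapy". It also summarises abnormal laboratory results by cycle, which 6.13.3 does not do for adverse events.

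**Timing.** Protocol 6.2.1: "The primary endpoint analysis will occur after the final patient enrolled has been evaluated for at least 1 cycle". Protocol 6.2 plans 2 cycles of treatment, but "Patients who are receiving benefit from study drug may continue to be treated" beyond that. The dose rationale in Protocol Section 5 reports that 15 patients had been dosed every 2 weeks, and that the maximum tolerated dose for that schedule was known, when weekly dosing was introduced.

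**Use.** The primary objective (Protocol 5.2.1) covers both a dose and a schedule. Under Protocol 7.2.3 the RP2D discussion "will include an assessment of safety, PK, and PD data".

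**Grouping.** SAP 6.1: "Data analyses will be provided by dose levels and for all patients combined wherever appropriate". Schedule is not a grouping factor, and SAP 5.1 describes only the two-weekly regimen: "Eligible patients will receive LY3164530 as an infusion on Days 1 and 15 of each cycle".

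**The concern.** The proportion of patients who have ever had an event can only rise with time observed. Two groups with the same true risk will show different proportions if one has been watched for longer. Here the imbalance comes from the design: Schedule 1 opened first, the last patient may have 28 days of data at the primary analysis, and patients who benefit stay on drug.

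What is at stake is the choice among doses and schedules that have already passed the DLT criterion. The grid says whether a dose is acceptable, but it does not rank two acceptable regimens. Events excepted from the DLT definition (for example Grade 3 rash that resolves in the stated time), and everything after Cycle 1, appear mainly in the TEAE tables. Those tables therefore carry weight when the grid leaves a choice open.

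**Working it through.** The documents give no adverse event rate, accrual rate or time on treatment, so there is no stated figure to reproduce. The check asks how large an artefact unequal follow-up could produce when the true hazard is the same in both groups.

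**1. Length of the adverse event window.** Routine collection ends about 28 days after the last dose (Protocol 8.1.2.2.3). For the planned 2 cycles:
- Schedule 1: last dose on day 28 + 15 = 43, window to day 43 + 28 = 71.
- Schedule 2: last dose on day 28 + 22 = 50, window to day 50 + 28 = 78.
- Last patient at the primary analysis: as little as 28 days.

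**2. One patient at each extreme.** With constant risk p per cycle, incidence by day d is 1 − (1 − p)^(d/28).

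| Assumed p per cycle | By day 28 | By day 71 |
|---|---|---|
| 10% | 10% | 23.4% |
| 20% | 20% | 43.2% |
| 30% | 30% | 59.5% |

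This is not the bias in a table, because most patients in the newer group have more than 28 days.

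**3. Whole groups.** Assumptions: 15 Schedule 1 patients with complete follow-up; 10 or 20 Schedule 2 patients entering at 2 or 4 per month; data cut 28 days after the last entry; adverse event window of 28 days plus an exponential time on treatment with median m cycles, the same in both groups. The hazard in Cycle 1 is h = −ln(1 − p)/28 per day. Afterwards it is f·h, with f = 1 (constant) or f = 0.25 (front-loaded). With λ = ln 2/(28m):
- Complete follow-up: incidence = 1 − (1 − p)·λ/(λ + f·h).
- Cut u days after day 28, with e = exp(−(λ + f·h)·u): incidence = 1 − (1 − p)·[λ/(λ + f·h)·(1 − e) + e], averaged over patients with u = 0, 30.4/rate, 2 × 30.4/rate and so on.

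Example: p = 0.30, m = 2, f = 1, 10 patients at 4 per month. Then h = 0.01274 and λ = 0.01238. Complete follow-up gives 1 − 0.7 × 0.4928 = 65.5%. The Schedule 2 average at the cut is 48.1%. The gap is 17.4 points with identical true risk.

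| Median cycles on treatment | Smallest gap, p = 30% (front-loaded, 20 patients, 2/month) | Largest gap, p = 30% (constant, 10 patients, 4/month) | Range at p = 10% |
|---|---|---|---|
| 1 | 38% v 37%: 1 point | 54% v 45%: 9 points | under 1 to 5 points |
| 2 | 44% v 41%: 3 points | 65% v 48%: 17 points | 2 to 13 points |
| 4 | 54% v 45%: 8 points | 77% v 50%: 27 points | 5 to 25 points |

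(Gaps are taken before rounding the percentages.)

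**4. Onset timing.** At p = 30% and a median of 2 cycles, the front-loaded hazard gives 3 to 9 points and the constant hazard 6 to 17. If all onsets fell in Cycle 1 the gap would be 0, because every patient in the model has 28 days.

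**5. With a common window.** Counting Cycle 1 onsets only, the gap is 0. In this model it is also 0 at study completion, because time on treatment is assumed equal in the two groups.

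**The case against.** A reader might infer that the SAP compares the schedules with these tables and that they will favour Schedule 2. The documents do not support that. No comparison by schedule is planned, the SAP does not mention Schedule 2, and the analyses are descriptive. The same artefact could arise between doses. A reader might also infer that the DLT criterion for the RP2D is biased. It is not: DLTs are counted in Cycle 1 for both schedules (Protocol 7.2.2.1), and the grid uses only those counts.

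Other points limit the size:
- Calendar time since enrolment is not adverse event follow-up, which ends about 28 days after the last dose.
- The schedules enrol in parallel after the amendment (Protocol 6.2).
- The 15 early patients span 300 to 1250 mg and are not one comparator. If the levels were those of the sample schema, with at least 3 patients each at 300 and 600 mg and at least 2 at 1250 mg (the fewest that can give an unacceptable-toxicity decision), at most 15 − 8 = 7 were at 1000 mg. An RP2D needs at least 10, so 1000 mg would need later patients too.
- Sampling error is large. In the worked example the standard error of the difference is √(0.655 × 0.345/15 + 0.481 × 0.519/10) = 20 points, against a gap of 17.4. The gap is below its standard error in 22 of the 24 scenarios run at 30%.
- SAP 6.13.2 tabulates cycles received by dose level, and Protocol 6.2.1 updates secondary analyses at study completion.

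All of this stands as to size and certainty, but it does not remove the point. The artefact is systematic and adds to the noise. The cycles table shows that follow-up differs without correcting the event counts. The update at completion comes after the primary analysis, and it leaves no gap only if time on treatment is similar.

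**Conclusion.** The point holds as a limited one. SAP 6.13.3 offers only crude worst-grade counts over whatever follow-up exists, and the primary analysis can fall when that follow-up is unequal. If regimens are then read side by side for the RP2D and schedule, the more recently enrolled group can look safer than it is. The Cycle 1 DLT grid is untouched.

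At an assumed 30% per cycle and equal true hazard the group-level shortfall is about 1 to 27 points, and about 3 to 17 at a median of 2 cycles. The hazard, accrual rate and time on treatment are all assumptions. The model also gives every Schedule 1 patient complete follow-up, so including those enrolled in parallel would narrow the gap. Stronger wording, that follow-up is much longer on Schedule 1 or that the tables will mislead, goes beyond what the documents show.

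**What to change.** The SAP needs an update to cover Schedule 2 in any case. In that update, add to 6.13.3, for the RP2D review, TEAE tables by dose and schedule with a common window:

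1. Onset in Cycle 1, all treated patients.
2. Onset in Cycles 1 to 2, patients first dosed at least 56 days before the data cut. A by-cycle table with patients at risk as the denominator would serve instead.

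Show follow-up or cycles received per group beside each table, and keep the all-follow-up tables. Rates per 100 patient-cycles are optional: they are not neutral to follow-up if the hazard changes over time.

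The cost is SAP wording and a few tables from data already collected. The drawback is that the Cycle 1 to 2 table leaves out the most recently dosed patients.

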6.13.4. Deaths, Serious Adverse Events, and Other Notable Adverse Events

Deaths and other SAEs will be listed and summarised. Summaries for patients on therapy will include:

- Listing of Patients who Discontinued due to Adverse Events or Death
- Listing of Deaths Reported
- Listing of Serious Adverse Events

Reasons for death will be summarized separately for on-therapy and within 28 days of last dose of study drug/last visit. All SAEs will be summarized by preferred term.

6.13.5. Clinical Laboratory Evaluation

Laboratory data (including chemistry, hematology, and coagulation) will be summarized for all patients on therapy. Relevant hematology and chemistry laboratory values will be graded according to CTCAE Version 4.03. The grades will be summarized by the maximum grade over the entire study for all patients on therapy.

Abnormal laboratory results will be summarized for all patients on therapy by cycle. To the extent that they can be assessed according to CTCAE Version 4.03 specific grades, these abnormal lab results will be summarized by cohort and cycle independent of clinical findings determined by the investigator. International System of Units (SI units) will be presented in all outputs.

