6.1.1. Inclusion Criteria

Patients may be included in the study if they meet all of the following criteria during screening prior to first dose of study drug.

- [1] Have histological or cytological evidence of a diagnosis of cancer that is advanced and/or metastatic. The patient must be, in the judgment of the investigator, an appropriate candidate for experimental therapy (eg, available standard therapies have been used, the patient is not eligible for standard curative therapy, or the patient has refused standard therapies).
- [2] Have the presence of measurable and/or nonmeasurable disease as defined by the Response Evaluation Criteria in Solid Tumors (RECIST) version 1.1 (Eisenhauer et al. 2009).
- [3] Are ≥ 18 years of age.
- [4] Have given written informed consent prior to any study-specific procedures.
- [5] Have adequate organ function, including:
 - Hematologic: Absolute neutrophil count (ANC) $\geq 1.5 \times 10^9$ cells /L, platelets $\geq 100 \times 10^9$ /L, and hemoglobin ≥ 8 g/dL. Transfusions to meet enrollment criteria are not allowed in the 14 days preceding the first dose of study drug.
 - Hepatic: Bilirubin ≤ 1.5 times upper limits of normal (ULN), alanine aminotransferase (ALT), and aspartate aminotransferase (AST) ≤ 3 times ULN. If the liver has tumor involvement, AST and ALT equaling ≤ 5 times ULN are acceptable.
 - Renal: Serum creatinine ≤ 1.5 times ULN.
- [6] Have a performance status of ≤ 1 on the Eastern Cooperative Oncology Group (ECOG) scale.
- [7] Prior Treatments
 - **Systemic treatments:** Have discontinued previous systemic treatments for cancer and recovered from the acute effects of therapy. Prior to first dose of study treatment, patients must have discontinued:

- Cytotoxic therapies or targeted agents that are small molecule inhibitors for 5 half-lives or at least 28 days (whichever is shorter).
 - Mitomycin-C or nitrosourea therapy for at least 42 days.
 - Biologic agents (eg, antibodies) for at least 28 days.
 - At the discretion of the investigator, hormone-sensitive prostate cancer patients receiving gonadotropin releasing hormone agonist therapy and breast cancer patients on antiestrogen therapy (eg, an aromatase inhibitor) may have that treatment continued while they are enrolled in Study JNBA. However, the treatment should have been started at least 3 months prior to first dose of study drug.

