8.1.2. Adverse Events

Lilly has standards for reporting AEs that are to be followed regardless of applicable regulatory requirements that may be less stringent. A clinical study AE is any untoward medical occurrence in a patient or clinical investigation subject administered a pharmaceutical product and which does not necessarily have a causal relationship with this treatment. An AE can therefore be any unfavorable and unintended sign (including an abnormal laboratory finding), symptom, or disease temporally associated with the use of medicinal (investigational) product whether or not related to the medicinal (investigational) product. Any clinically significant findings from labs, vital sign measurements, and so on that occur should also be reported to Lilly or its designee as

an AE. Lack of drug effect is not an AE in clinical studies because the purpose of the clinical study is to establish drug effect.

The investigator, monitor, and Sponsor will review the collected data regularly for evidence of AEs. All patients will be assessed routinely for AEs as outlined in the study schedule. All AEs observed will be graded using CTCAE v 4.03.

The CTCAE v 4.03 will serve as the reference document for choosing appropriate terminology for, and grading the severity of, all AEs and other symptoms. All AEs observed will be graded using CTCAE v 4.03. Any minor version of CTCAE v 4.0 (eg, v 4.03) may be used for this study. Minor CTCAE v 4.0 updates from the NCI will not necessitate a protocol amendment. For AEs without matching terminology within the CTCAE v 4.03 criteria, the investigator will be responsible for selecting the appropriate system organ class and assessing severity grade based on the intensity of the event. Note that both CTCAE term (actual or coded) and severity grade must be selected by study site personnel and collected on the eCRF. This collection is in addition to verbatim text used to describe the AE.

In addition to collecting the AE verbatim, the CTCAE term, and the CTCAE severity grade, AE verbatim text will also be mapped by the Sponsor or designee to corresponding terminology within the Medical Dictionary for Regulatory Activities (MedDRA) dictionary.

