8.1.2.2.3. Follow-Up Visit

All AEs and SAEs, regardless of relatedness to study drug or protocol procedures, occurring during the follow-up visit (Visit 801) must be reported to Lilly or its designee. The follow-up visit starts following the last dose of study drug. At the end of the follow-up visit, the patient will be required to have specific safety assessments ([Attachment 1](#)). The timing of these assessments is 28 days \pm 5 days after the last dose of study drug.

If it is deemed to be in the best interest of the patient to start a new anti-cancer treatment prior to the scheduled end of the follow-up visit period, the follow-up visit duration may be shortened. In this case, follow up assessments, including AE and SAE reporting should be completed prior to the initiation of the new therapy.

Following the safety assessments that mark the planned end of the follow-up visit (Visit 801), the patient will be discontinued from the study, unless there is an ongoing AE or SAE that is possibly related to study drug. Particular focus should be placed on patients that have abnormal electrolytes, as electrolyte depletion is known to occur for >6 weeks after EGFR monoclonal antibody therapy.

If a patient has an ongoing AE or SAE possibly related to LY3164530 (eg, abnormal electrolytes), the patient should be followed until the event is resolved, the event is no longer considered to be study drug-related, the event becomes stable or returns to baseline, a new treatment is initiated for the patient, or the patient dies or is lost to follow-up. Any subsequent follow-up(s) for AEs will be no more than 28 days \pm 5 days in duration.

After the follow-up visit (Visit 801), AEs are not required to be reported unless the investigator feels the AEs were related to either study drug, drug delivery system, or a protocol procedure. If an investigator becomes aware of an SAE believed to be related to protocol procedures or study drug, the investigator should report the SAE to the Sponsor ([Attachment 6](#)), and the SAE will be entered in the Lilly Safety System.

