Baseline	For change from baseline analyses, baseline value is defined as the last reported measure on or before the first dose (prior to the dose administration). For change from baseline within a cycle, the measure prior to the first dose of that cycle is baseline. If more than one pre-dose measure is available, they may be averaged if appropriate.
Entered	Patients who sign the informed consent document (ICD).
Enrolled	Patients who have been assigned to a treatment (assigned means they received ≥ 1 dose for this study).

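### The laboratory grade tables take no account of baseline grade, so they cannot separate treatment-emergent from pre-existing abnormalities

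*SAP*

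**What the plan says.** SAP 6.13.5 plans two summaries of graded laboratory data. The first takes the worst grade per patient: "The grades will be summarized by the maximum grade over the entire study for all patients on therapy". The second concerns abnormal results: "these abnormal lab results will be summarized by cohort and cycle independent of clinical findings determined by the investigator". The section mentions no baseline grade, shift table or treatment-emergent rule, and does not exclude pre-dose values. Protocol 10.4 adds only that laboratory values will be summarized.

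Table JNBA.6.1 in SAP 6.1 does define a baseline, the last measure before the first dose, but for change-from-baseline analyses. SAP 6.13.5 does not call on it.

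The adverse event analysis is built differently. Under SAP 6.13.3 a treatment-emergent adverse event (TEAE) is either an event arising after dosing or "adverse events already present during screening that worsen following exposure to the treatment, regardless of causality".

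On entry, Protocol 6.1.1 allows AST and ALT up to 3 times ULN and adds: "If the liver has tumor involvement, AST and ALT equaling ≤ 5 times ULN are acceptable". It allows bilirubin and creatinine up to 1.5 times ULN and hemoglobin down to 8 g/dL, and it gives no limit for any electrolyte. The washout for earlier antibody treatment is "Biologic agents (eg, antibodies) for at least 28 days". Protocol 8.1.2.2.3, on follow-up after the last study dose, remarks that "electrolyte depletion is known to occur for >6 weeks after EGFR monoclonal antibody therapy".

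**The concern.** A maximum grade with no baseline beside it mixes three kinds of patient: those who became abnormal on LY3164530, those who entered abnormal and got worse, and those who entered abnormal and stayed the same. The third group says nothing about the drug, yet it has the same weight in the table.

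This matters because describing the safety and toxicity profile is a secondary objective (Protocol 5.2.2) and the study has no control arm. The patient's own baseline is then the main means of telling new abnormality from old. Dose and schedule groups are small (at least 3 patients per dose, 10 to 20 at the recommended Phase 2 dose), so a chance difference in who entered abnormal could look like an effect of dose or schedule.

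**Working it through.** The plan gives no figure to reproduce on this point. The check has four steps.

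**1. Where the plan uses baseline and where it does not**

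| Analysis or rule | Reference to baseline |
|---|---|
| TEAEs (SAP 6.13.3) | Yes: a pre-existing event counts only if it worsens |
| ECG categories, if triggered (SAP 6.13.7) | Yes: compared with Cycle 1 Day 1 pre-dose |
| Hepatic monitoring (Protocol 8.1.4) | Yes: for patients entering with ALT at or above 3 times ULN, trigger at 2 times baseline |
| Criteria before each cycle (Protocol 7.2.5.1) | Yes: recovery to Grade 1 or less, or to baseline |
| Laboratory grades (SAP 6.13.5) | None |

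The protocol clearly expects some patients to enter abnormal. The laboratory tables do not carry that through.

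**2. Is a baseline comparison feasible?** Yes. Protocol Attachment 4 collects hematology and chemistry at screening and pre-dose on Cycle 1 Day 1, then repeatedly after dosing. The chemistry panel in Attachment 2 includes liver tests, magnesium, calcium, potassium and sodium.

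**3. Timing for electrolytes**
- Stated duration of depletion after an EGFR antibody: more than 6 × 7 = 42 days.
- Minimum antibody washout: 28 days.
- Difference: 42 − 28 = 14 days, half of the 28-day Cycle 1.
- If the first study dose falls 28 days after the last antibody dose, day 42 is study day 42 − 28 + 1 = 15 on the SAP's day count. The post-dose chemistry samples on Days 1, 2, 3 and 8 precede it.

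Overlap is therefore possible for a patient entering near the minimum washout. A longer washout shortens or removes it.

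**4. Illustration of size.** Let b be the share of patients abnormal on a given test at entry, and t the new-onset rate among patients normal at entry. The documents give neither; all values here are assumptions.

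The chance that a cohort of n includes at least one patient abnormal at entry is 1 − (1 − b)^n:

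| b | n = 3 | n = 10 | n = 20 | Expected among 50 |
|---|---|---|---|---|
| 5% | 14% | 40% | 64% | 2.5 |
| 10% | 27% | 65% | 88% | 5 |
| 20% | 49% | 89% | 99% | 10 |

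If entry abnormalities persist into at least one counted value, the tabulated any-grade rate is b + (1 − b)t. With t = 10%:
- b = 5%: 0.05 + 0.95 × 0.10 = 14.5%, of which new onset is 0.95 × 0.10 = 9.5%.
- b = 20%: 0.20 + 0.80 × 0.10 = 28%, of which new onset is 0.80 × 0.10 = 8%.

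Two groups with the same drug effect would show 14.5% and 28% only because different patients entered. Worsening in patients already abnormal would add to the treatment-emergent part and is left out of this sketch.

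**The case against.** **The table is descriptive.** A reader might infer that the plan counts pre-existing abnormalities as LY3164530 toxicity. The documents do not support that. SAP 6.13.5 assigns no cause and does not call the grades treatment-emergent or drug-related. The weakness is that the table cannot make the distinction. This part of the objection stands.

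**Adverse event and DLT analyses already deal with worsening and relatedness.** They do: TEAEs require onset or worsening after dosing, and a DLT requires at least possible relatedness. Protocol 8.1.2 also sends some laboratory findings to the adverse event route: "Any clinically significant findings from labs, vital sign measurements, and so on that occur should also be reported to Lilly" or its designee as an adverse event. But only clinically significant findings take that route, and asymptomatic Grade 3 or 4 electrolyte abnormalities that respond to standard treatment are exempt from the DLT definition. For the rest, the laboratory tables may be the main systematic view. A reader might also infer that DLT counts or the escalation rules are affected. They are not, because neither uses this table.

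**The carry-over is inferred.** A reader might take the protocol to say that effects of earlier EGFR antibody treatment outlast the washout. It does not say so. The remark on depletion explains follow-up after the last study dose, concerns electrolytes only, and does not say that every treated patient is depleted. Protocol 6.1.1 also requires recovery from the acute effects of earlier therapy. What remains is a possibility, read from two separate sections.

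**The phrase about patients on therapy may already exclude screening values.** It can be read as naming the patients or the period, and the reference to the whole study points the other way. Even on the narrow reading, an abnormality that continues unchanged after the first dose is still counted.

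**A shift table can be added later.** SAP 6.1 allows further exploratory analyses, so this is true, but the plan does not commit to one.

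**Conclusion.** The point holds as a gap in the laboratory summaries. As written, SAP 6.13.5 cannot separate treatment-emergent from pre-existing abnormalities, although eligibility admits abnormal values and the data and baseline definition needed are already in place. Where an entry limit exists, it caps how abnormal a pre-existing value can be. Electrolytes have no such cap, and carry-over from a recent EGFR antibody is possible for them.

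The size cannot be derived from the documents, which report neither rates of abnormality at entry nor how many patients had an EGFR antibody or how recently. The 5% to 20% range and the 10% new-onset rate are assumptions that show the mechanism only. The primary objective, the DLT counts and the escalation grid are untouched. The reason to act is a clearer toxicity profile at little cost.

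**What to change.** In SAP 6.13.5:

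- Restrict the maximum grade to values taken after the first dose.
- Add a shift table for each graded hematology and chemistry test: baseline grade against worst post-dose grade, by schedule and dose. Use the SAP 6.1 baseline before the first study dose, not the within-cycle one, and take the last value without averaging.
- Call a laboratory abnormality treatment-emergent only when the post-dose grade exceeds the baseline grade, and apply the same rule to the summary by cohort and cycle.
- Tabulate low and high abnormalities separately for tests that can move either way.
- Show patients with no baseline or no post-dose value as missing, since SAP 6.3 rules out imputation.

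The margin of the shift table still gives the maximum post-dose grade, so that information is kept. A separate line for patients with a recent EGFR antibody is optional. Its cells would be very small, and SAP 6.8 does not list the date of the last earlier dose among the prior-therapy items.

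The cost is SAP wording and one more table program. Reported counts of laboratory toxicity may be lower. No sample, visit or eligibility rule changes.
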